8.2. Patients' features

All diabetic patients undergoing coronary angiography will be screened for the enrollment in the present study.

Inclusion criteria:

We will include diabetic patients treated with metformin undergoing coronary angiography.

Exclusion criteria:

All patients presenting the following features will be excluded from the study:

- 1. Known coronary anatomy with planned complex percutaneous coronary intervention with high probability of large amount of contrast use (>150 ml).
- 2. Moderate to severe impairment of renal function (eGFR<45 ml/min).
- 3. Moderate to severe impairment of liver function (Child-Pugh class B or C).
- 4. Severely impaired left ventricular ejection fraction (LVEF <35%).
- 5. Patients undergoing primary percutaneous coronary intervention (i.e., patients presenting with ST elevation myocardial infarction).
- 6. Severe to very severe chronic obstructive pulmonary disease (GOLD class 3 to 4).
- 7. Patients scheduled for cardiac surgery in the following 5 days.
- 8. Inability to provide informed consent.

9. STUDY PROCEDURE

The aim of the study is to evaluate if metformin continuation in diabetic patients undergoing coronary angiography could lead to an increase in lactic acid values. Clinical, laboratoristic, and echocardiographic data will be collected in order to evaluate the presence and the eventual impact on the risk of increased lactic acid values. All these data will be collected in an anonymous form at the Cardio Center of the Humanitas Research Hospital, [name]. We will add lactic acid to all the routinely laboratoristic parameter collected before and after coronary angiography in our center.

9.1. Patients instructions

All patients potentially enrolled will be informed regarding the study and will have to sign an informed consent before the inclusion in the study. A time schedule of study procedure is resumed in Table 1.1

9.2. Pre-enrollment and pre-procedure evaluation (baseline)

Before the inclusion, all patients will undergo to:

- 1. Medical history and physical examination;
- 2. Hemocrome, kidney and liver function, lactic acid evaluation at venous sample;
- 3. CK-MB, hs-troponin I, BNP evaluation at venous sample;
- 4. Transthoracic echocardiography;
- 5. 12-leads electrocardiogram.

9.3. Post-procedure evaluation (the same day after coronary angiography and before hospital discharge)

During postprocedure monitoring (after coronary angiography and before discharge) the following clinical,

laboratoristic, and echocardiographic data will be collected:

- 1. Hemocrome, kidney and liver function, lactic acid evaluation at venous blood sample;
- 2. CK-MB, hs-troponin I, BNP evaluation at venous blood sample;
- 3. Transthoracic echocardiography;
- 4. 12-leads electrocardiogram.
- 5. Lactic acidosis, death, kidney failure, liver failure

9.4. Follow up

All patients will undergo a venous blood sample and will be contacted by phone call (if already discharged) to collect the following data:

- 1. Hemocrome, kidney and liver function, lactic acid evaluation at venous blood sample;
- 2. Lactic acidosis, death, kidney failure, liver failure

Visit schedule and data that will be collected are resumed in Table 1.1.

10. ADVERSE EVENT RISK/BENEFIT NOTIFICATION

10.1. Adverse event

According to the 2018 ESC guidelines on myocardial revascularization and literature data, there should not be an augmented risk for lactic acidosis in those patients that will satisfy our inclusion and exclusion criteria.

10.2. Cause of study withdrawal

All patients that will develop CIN will suspend metformin, as recommended by the 2018 ESC guidelines on myocardial revascularization.

11. STATISTICAL ANALYSES

11.1. Methods

Continuous variables will be reported as mean \pm standard deviation and compared with Student's t test or Mann–Whitney or Wilcoxon tests on the basis of normality of data verified by Kolmogorov–Smirnov goodnessof-fit test. In case of non-normal distribution, variables will be reported as median and interquartile range (IQR). For the primary endpoints of postprocedure lactic acid values, also 95% confidence intervals will be reported. Categorical variables are reported as N (%) and will be compared with χ^2 test without Yates correction for continuity or the Fisher exact test as appropriate. Subgroup analyses will be performed to assess eventual differences in the following subgroups:

- Patients taking other antiglycaemic drugs on top of metformin.
- Patients requiring percutaneous coronary angioplasty.
- Patients with mild and moderate renal function impairment (eGFR<90 and <60 ml/min).

- Patients undergoing urgent coronary angiography (<24 hours from the index event).

Furthermore, linear regression will be performed to assess the correlation between clinical, laboratoristic, and echocardiographic variables with postprocedural lactic acid values.

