1 PROTOCOL SYNOPSIS

Study title	Metformin continuation safety in diabetic patients undergoing coronary			
•	angiogra p hy.			
Acronym	NO-STOP			
IRCCS internal sites:	Cardio Center, IRCCS Istituto Clinico Humanitas – [name]			
IRCCS external sites:	None			
Population	Diabetic patients treated with metformin undergoing coronary angiography.			
Objectives	To assess the safety of metformin in diabetic patients undergoing coronary angiography in terms of risk of lactic acidosis. Individuate eventual clinical, echocardiographic predictors of lactic acidosis in this setting.			
Study design	Prospective, no-profit, single arm trial, powered for non-inferiority with respect to historical cohort.			
Sample size	The study require the enrollment of at least 110 patients.			
Primary endpoint	Increase of 20% from preprocedural lactic acid values.			
Secondary endpoints	Contrast-associated acute kidney injury after coronary angiography. Lactic acidosis development after coronary angiography. Correlation between clinical, laboratoristic, and echocardiographic variables and lactic acid values.			
Inclusion criteria	Diabetic patients treated with metformin undergoing coronary angiography.			
Exclusion criteria	Known coronary anatomy with planned complex percutaneous coronary intervention with high probability of large amount of contrast use (>150 ml). Moderate to severe impairment of renal function (eGFR<45 ml/min). Moderate to severe impairment of liver function (Child-Pugh class B or C). Severely impaired left ventricular ejection fraction (LVEF <35%). Patients undergoing primary percutaneous coronary intervention (i.e., patients presenting with ST elevation myocardial infarction). Severe to very severe chronic obstructive pulmonary disease (GOLD class 3 to 4). Patients scheduled for cardiac surgery in the following 5 days. Inability to provide informed consent.			
Prespecified	Patients taking other antiglycaemic drugs on top of metformin.			
subgroup analyses	Patients requiring percutaneous coronary angioplasty. Patients with mild and moderate renal function impairment (eGFR<90 and <60 ml/min). Patients undergoing urgent coronary angiography (<24 hours from the index event).			
Follow-up	The days after coronary angiography, at discharge and after three days from coronary angiography.			

CONFIDENTIAL

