8. STUDY POPULATION

8.1. Sample size

In our historical cohort of diabetic patients taking metformin, we observed a mean value of lactic acid of 1.2+0.7 mmol/l.

A total of 106 patients in an estimated time of one years are planned to be enrolled in order to detect with 90% power a prespecified increase of lactic acid of 20% from preprocedural values with a probability of alpha error of

0.05.

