11.2. Level of significance

Statistical test will be used to:

- to refuse the null hypothesis of lack of association between metformin continuation and postprocedural increase of lactic acid of 20% from baseline values (primary endpoint) and our secondary endpoints (Ho = metformin continuation not associated with the endpoint)

Association between variables or events will be set at probabilistic level of 5% (p value< 0.05)

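### If a subgroup is a minority with a different lactate spread, Student's t chosen on normality alone will not hold the 5% level; naming Welch's t is a cheap improvement

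*Combined protocol and SAP*

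**What the plan says.** Section 11.1 states that continuous variables will be "compared with Student's t test or Mann–Whitney or Wilcoxon tests on the basis of normality of data", with normality judged by a Kolmogorov-Smirnov test. Normality is the only property checked. No variance check is planned and Welch's test is not mentioned.

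The same section then says "Subgroup analyses will be performed to assess eventual differences in the following subgroups" and lists four factors: other antiglycaemic drugs, angioplasty, reduced eGFR (below 90 and below 60) and urgent angiography. It attaches no test to them. It also does not say whether a subgroup is compared with its complement or pre- with post-procedure values inside each subgroup.

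Section 11.2 sets the level at 5%. Section 8.1 gives the only information on spread: "we observed a mean value of lactic acid of 1.2+0.7 mmol/l". That is one overall figure for lactate levels. No SD is given for the change in lactate or for any subgroup, and no subgroup size is given.

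**The concern.** Student's t conventionally means the pooled-variance form, which assumes equal SDs in the two groups. When group sizes differ, the pooled SD is dominated by the larger group. If the smaller group is more variable, the standard error is too small and the test rejects too often. If the smaller group is less variable, the standard error is too large and real differences are missed.

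Minority subgroups are plausible here. The exclusion of eGFR below 45 confines the eGFR below 60 subgroup to 45-59, and urgent angiography excludes ST-elevation patients treated by primary intervention. Identifying predictors of raised lactate is a stated objective (section 4). A subgroup falsely flagged as higher-risk, or one that is missed, would bear on how the safety result is read.

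**Working it through.** **Inputs from the plan.** N = 106 (section 8.1; the synopsis says at least 110). Alpha 5% (section 11.2), taken as two-sided.

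**Assumptions.** Smaller group n1 of 106; SD ratio r = smaller group's SD / larger group's SD; normal data; no true difference.

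**1. Reproduce the stated 5%.** With r = 1, simulated pooled t rejects in 4.9-5.1% at every split tried, from 11/95 to 53/53. At 53/53 it stays near 5% for every r from 0.5 to 2. So the plan's figure holds under either condition.

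**2. Why it moves otherwise.** Set the larger group's SD to 1.
- Squared standard error used by the pooled test, on average: [((n1−1)r² + (n2−1))/(N−2)] × (1/n1 + 1/n2).
- True squared standard error: r²/n1 + 1/n2.

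For n1 = 16, n2 = 90, r = 2:
- Used: (15×4 + 89)/104 = 1.433; times (1/16 + 1/90) = 0.0736 gives 0.1055.
- True: 4/16 + 1/90 = 0.2611.
- Standard error too small by √(0.2611/0.1055) = 1.573. The critical value 1.983 acts like 1.983/1.573 = 1.26, a two-sided tail of about 21%.

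For r = 0.67:
- Used: (15×0.449 + 89)/104 × 0.0736 = 0.0678.
- True: 0.449/16 + 1/90 = 0.0392.
- Factor 0.760; 1.983/0.760 = 2.61, a tail of about 0.9%.

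**3. Simulated false-positive rate of the pooled t** (40,000 runs per cell; repeat runs differ by up to about half a percentage point).

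| Smaller group | r = 0.67 | r = 1 | r = 1.25 | r = 1.5 | r = 2 |
|---|---|---|---|---|---|
| 11 | 0.8% | 5.1% | 9.8% | 15.4% | 24.6% |
| 16 | 1.0% | 4.9% | 9.5% | 13.7% | 21.0% |
| 21 | 1.4% | 5.1% | 8.6% | 12.2% | 18.0% |
| 26 | 1.8% | 5.0% | 8.2% | 11.0% | 15.6% |
| 32 | 2.3% | 5.1% | 7.1% | 9.3% | 12.3% |
| 42 | 3.4% | 5.1% | 6.0% | 7.1% | 8.5% |
| 53 | 5.3% | 5.0% | 5.0% | 4.8% | 5.0% |

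Welch's t stays at 4.8-5.3% throughout.

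**4. Power.** For a difference of 0.5 SD of the larger group and r = 0.67, pooled t has about 47% against 68-69% for Welch at n1 = 16, and 69% against 82% at n1 = 26. With equal SDs the order reverses slightly: 45% pooled against 42% Welch at 16, and 59% against 58% at 26.

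**5. The normality screen.** With normal data, the Kolmogorov-Smirnov test with estimated mean and SD rejects in 0-1% of runs, so Student's t is used and its error is unchanged. With lognormal lactate (mean 1.2, SD 0.7) it rejects in 35-89% of runs, and those comparisons go to Mann-Whitney. Mann-Whitney is not immune: with normal data it rejects in about 7-11% at r = 1.5 and 2 for smaller groups of 16 and 26.

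**6. Limit of the remedy.** With lognormal data and r = 2, Welch on the raw scale rejects equal means in 7.7-13.0%.

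**The case against.** A reader might infer that the subgroup p-values and confidence intervals are simply wrong, with a real error rate well away from 5%. The documents do not support that, for several reasons.

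- They give no subgroup sizes or SDs. Angioplasty, add-on drugs or eGFR below 90 need not define small groups. Near an even split the effect is slight: 42 of 106 at a ratio of 1.5 gives 7.1%.
- Section 11.1 neither says pooled nor ties Student's t to the subgroups. A pre/post comparison within a subgroup would be paired and unaffected. Categorical outcomes go to chi-square or Fisher tests. Still, Mann-Whitney is a test for independent groups, and in a single-arm study the listed subgroups are the obvious groups to compare.
- It is tempting to argue from 0.7/1.2 = 0.58 that a subgroup with higher lactate has a larger SD. If SD follows the mean, equal means imply equal SDs, and the 5% level holds. A ratio of 1.5 would need means of 1.8 against 1.2, which is a real difference, not a false positive. What survives is interval coverage when means do differ: at SD ratios of 1.25-1.5 a pooled 95% CI covers only about 86-92% (100 − 13.7 = 86.3 at n1 = 16, ratio 1.5; 100 − 8.2 = 91.8 at n1 = 26, ratio 1.25). However, section 11.1 promises intervals only for the primary endpoint.
- Skewed lactate would often be sent to Mann-Whitney, so the Student figures would not apply to those comparisons.

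All of this stands. It makes the point conditional but leaves the omission in place: nothing in section 11.1 guards against unequal spread when Student's t is used.

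**Conclusion.** The point holds as a conditional one. If a subgroup is both a minority and differently spread, and its lactate is compared with the complement by pooled t, the error rate departs from 5%. For a smaller group of 26 or 16 it is about 8-10%, 11-14% and 16-21% at SD ratios of 1.25, 1.5 and 2, and 1-2% with lost power at 0.67. With equal SDs or an even split it is about 5%. These figures rest on normal data, N = 106, two-sided testing and assumed shares and ratios. The primary endpoint, a within-patient change, is not touched, and subgroup results are not among the listed endpoints. This is a cheap improvement to secondary comparisons, not a flaw in the main result.

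**What to change.** In section 11.1, add that a continuous variable (for example, the change in lactate) compared between a subgroup and its complement will be analysed by Welch's unequal-variance t test with its 95% CI, in place of Student's t and without a preliminary variance test. State that contrast explicitly. If lactate is skewed, apply the test to log-lactate, as the log ratio of post- to pre-procedure values, because Welch alone is not a full remedy for skewed data.

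The cost is a line or two of wording and no new data. When SDs are in fact equal, the power loss for a 0.5 SD difference is about 3 points at a subgroup of 16 (45% to 42%) and about 1 point at 26 (59% to 58%).

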7. ENDPOINTS

7.1. Primary endpoint

An increase of lactic acid of 20% from preprocedural values in patients undergoing coronary angiography without discontinuing metformin.

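### Section 11.1 lets a normality test choose between mean and median for lactate; one paired ratio analysis, fixed in advance, would match the 20% endpoint

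*Combined protocol and SAP*

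**What the plan says.** Section 7.1 defines the primary endpoint on a relative scale: "An increase of lactic acid of 20% from preprocedural values in patients undergoing coronary angiography without discontinuing metformin". The synopsis gives the same 20% rise and describes a single-arm trial powered for non-inferiority.

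Section 8.1 gives the only lactate figures: "we observed a mean value of lactic acid of 1.2+0.7 mmol/l". It plans 106 patients "in order to detect with 90% power" "a prespecified increase of lactic acid of 20% from preprocedural values", with alpha 0.05.

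Section 11.1 holds the analysis rule for continuous variables. The test is Student's t, Mann–Whitney or "Wilcoxon tests on the basis of normality of data verified by" a Kolmogorov–Smirnov test. Mean and SD give way to median and interquartile range if normality is rejected. On the primary endpoint it adds only this: "For the primary endpoints of postprocedure lactic acid values, also 95% confidence intervals will be reported". It does not say:

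- whether baseline, post-procedure or change values are tested for normality;
- whether the critical values are corrected for an estimated mean and SD;
- which test, scale or summary applies to lactate.

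Section 11.2 adds a 5% significance level. No log or ratio analysis is planned anywhere.

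**The concern.** The endpoint is a percentage rise within patients. Because no lactate analysis is named, lactate analysed as a continuous variable falls under the normality rule, and what is estimated is settled only once the data are in. One branch reports a mean in mmol/l and the other a median in mmol/l. For skewed data these are different quantities, and neither is a relative change.

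Two analysts could both follow Section 11.1 faithfully, one testing baseline values and the other testing changes, and report different primary results from the same trial. At stake is whether the reported interval can answer the protocol's own question of a rise of 20%.

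**Working it through.** **Inputs.** Mean 1.2 and SD 0.7 mmol/l (Section 8.1, reading the plus sign as plus/minus); a 20% rise; n = 106; 90% power; alpha 0.05. Not in the documents and therefore assumed: the shape of the lactate distribution (lognormal unless stated) and the pre/post correlation (0.3 to 0.7 on the log scale, unless a wider range is given).

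**The plan's own figure.** The target difference is 0.20 × 1.2 = 0.24 mmol/l. The paired formula n = (SD × (1.960 + 1.282)/0.24)², with 0.7 taken as the SD of the change, gives 89.4, so 90 (92 with the t distribution). It does not give 106. Two unstated variants do:

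- dividing the t-based 91.3 by 0.864, the minimum relative efficiency of the signed-rank test: 91.3/0.864 = 105.7;
- allowing for 15% loss: 90/0.85 = 105.9.

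The sample size therefore does not reveal which branch of the rule the sponsor had in mind.

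**Is skew foreseeable?** The SD is 0.7/1.2 = 58% of the mean. A normal curve puts Φ(−1.2/0.7) = Φ(−1.714) = 4.3% of values below zero, which is impossible for lactate. A lognormal with the same moments has log-variance ln(1 + (0.7/1.2)²) = ln(1.340) = 0.293, log-SD 0.541, median 1.2/√1.340 = 1.04 and skewness 1.95.

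**Which branch would be taken?** Simulated rejection rates at n = 106 with lognormal lactate:

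| Values tested | Uncorrected Kolmogorov–Smirnov | With Lilliefors critical values |
|---|---|---|
| Baseline lactate | about 57% | about 98% |
| Paired changes | about 7% to 20% | 51% to 75% |

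The corrected figures for changes cover correlations from 0 to 0.7. The branch depends heavily on two choices that Section 11.1 leaves open.

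**What would each branch report?** For a true 20% rise, the mean change is 1.44 − 1.20 = 0.24 mmol/l. The median change, by simulation, is about 0.19 mmol/l. As a percentage, 0.19 is 0.19/1.2 = 16% of the baseline mean or 0.19/1.04 = 18% of the baseline median, not 20%. The mean does convert to 20%, but its interval in mmol/l must first be divided by a baseline mean that is itself estimated. The mean of log(post/pre), back-transformed, gives 1.20 directly, with an interval on the same scale.

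**Does a log-ratio test have more power?** Simulated power against no change, for a true ratio of 1.2 at n = 106:

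| Distribution, correlation | Paired t | Signed-rank | Log-ratio t |
|---|---|---|---|
| Lognormal, 0.3 | 76% | 79% | 83% |
| Lognormal, 0.5 | 86% | 89% | 93% |
| Gamma, 0.3 | 77% | 73% | 69% |
| Gamma, 0.5 | 87.5% | 85.5% | 83.6% |

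The sign of the difference reverses between two distributions with the same mean and SD. The type I error of the two-stage procedure was 4.2% to 6.1%.

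**The case against.** The strongest objection is that Section 11.1 names no test for the primary endpoint, so it is an inference that the normality rule governs it. Sections 7.1 and 11.2 can also be read as a patient-level event, a rise of at least 20%. The categorical rules would then apply, the normality test would be irrelevant, and a mean log-ratio would estimate the wrong quantity. This stands, and the point is limited to the average-change reading. It is also fair that Section 8.1 states lactate as an arithmetic mean, so a ratio of geometric means is a natural choice but not the only defensible one.

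A reader might also infer several stronger claims that the documents do not support:

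- *The fixed log-ratio analysis is more powerful.* It gains about 1 to 7 points with lognormal data and loses about 1 to 8 with gamma data. The documents do not say which shape applies.
- *Pre-testing inflates the false-positive rate.* It stayed near 5%.
- *The Kolmogorov–Smirnov test almost never rejects.* That holds for the uncorrected test on truly normal data (about 0.02% instead of 5%), not for skewed baseline lactate.
- *The two branches contradict each other unusually often.* For a true 10% rise with lognormal data, t and signed-rank disagree on significance in about 11% to 14% of trials. Log-ratio and signed-rank disagree in 9.5% to 11.8%, which is little better.
- *Listing Mann–Whitney is an error.* The sentence covers continuous variables in general, and the planned subgroup comparisons are unpaired.

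**Conclusion.** The point holds in a limited form. If the primary endpoint is an average change, Section 11.1 leaves its estimand and interval to a normality test applied to unspecified values. Under the lognormal assumption, the chance of leaving the mean branch runs from about 7% to about 57% with the uncorrected test, depending on which values are tested. The reported effect of a true 20% rise moves between about 0.24 and 0.19 mmol/l. Neither branch gives an interval directly comparable with 20%.

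The foreseeable skew follows from the protocol's own mean and SD. The rejection rates and the 0.19 rest on the assumed lognormal shape and correlation. This is a matter of prespecification and of matching the analysis to the endpoint: a worthwhile, cheap improvement, not a threat to the trial's error rates.

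**What to change.** In Section 11.1, exempt lactate from the normality rule and state one primary analysis, along these lines: the primary analysis is the mean of per-patient log(post/pre) lactate with a 95% confidence interval from a paired t, back-transformed to a ratio of geometric means and compared with 1.20; the Wilcoxon signed-rank test is a sensitivity analysis.

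First state which reading of Section 7.1 is meant. If it is the share of patients with a rise of at least 20%, make that proportion with its 95% confidence interval the primary analysis instead.

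The power figures above are for a test against no change, so they do not carry over to a comparison with 1.20. In a lognormal simulation at correlation 0.3 and n = 106, the upper limit fell below 1.20 in 82% of trials when the true ratio was 1.0, 29% when it was 1.1 and under 3% when it was 1.2. The sponsor should state the operating characteristics of whichever comparison is chosen.

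The cost is one paragraph and no new data. The downside is that results appear as ratios; a descriptive mean and median change in mmol/l can be given alongside.

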1.1. TIME SCHEDULE

Event	Screening	Post-procedure	At discharge	At three days
Type of contact with the patient	Visit		Visit	Visit/phone call
Inclusion/exclusion criteria	х			
Informed consent	х			
Medical hystory	х			
Physical examination	х	х	х	
Hemocrome, kidney and liver function, lactic acid	х	х	х	х
CK-MB, hs-troponin I, BNP	х	х	x	
Transthoracic echocardiography	х			
12-leads electrocardiogram	х	х	x	
Lactic acidosis, death, kidney failure, liver failure		Х	х	Х

NO-STOP protocol

CONFIDENTIAL

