5. STUDY DESIGN

The study is designed as a prospective, observational, single arm study.

Enrollment timing: enrollment rate will determine the duration of the study. We estimate that one year will be sufficient to achieve this objective.

Enrollment center: the study will be conducted at the Cardiac Center of the Humanitas Research Hospital, [name].

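### The primary endpoint is a 20% rise in lactic acid from baseline, but the planned 95% CI is for the post-procedure level, and the plan gives the rise neither a CI nor a comparison with 20%

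*Combined protocol and SAP*

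**What the plan says.** - **Endpoint (7.1; the synopsis agrees):** "An increase of lactic acid of 20% from preprocedural values in patients undergoing coronary angiography without discontinuing metformin".
- **Sizing (8.1):** the study is to "detect with 90% power a prespecified increase of lactic acid of 20% from preprocedural values", with 106 patients and an alpha error of 0.05. The only variability given is for a level: "In our historical cohort of diabetic patients taking metformin, we observed a mean value of lactic acid of 1.2+0.7 mmol/l".
- **Interval (11.1):** "For the primary endpoints of postprocedure lactic acid values, also 95% confidence intervals will be reported". The section lists Student's t, Mann–Whitney and Wilcoxon tests, chosen by a normality check. It does not say whether the primary comparison is paired, and it defines no change, ratio or proportion.
- **Null hypothesis (11.2):** "lack of association between metformin continuation and postprocedural increase of lactic acid of 20% from baseline values (primary endpoint"), tested at the 5% level with sidedness not stated.
- **Design:** the synopsis says "Prospective, no-profit, single arm trial, powered for non-inferiority with respect to historical cohort"; section 5 says "The study is designed as a prospective, observational, single arm study".
- **Samples (1.1):** the row "Hemocrome, kidney and liver function, lactic acid" is marked at screening, post-procedure, discharge and three days.

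**The concern.** The quantity that receives an interval is not the quantity that defines the endpoint. A post-procedure level does not use the patient's baseline, so its CI cannot show how far lactic acid rose.

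The null in 11.2 does not repair this. It concerns an association with continuing metformin, but the study has no group that stops the drug, so there is nothing to contrast.

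Three readings of the primary result therefore remain open: the group's rise from its own baseline (8.1, 11.2), a comparison with the historical cohort (synopsis), or the share of patients whose value rises by 20% (7.1 can be read per patient). The synopsis speaks of non-inferiority, which means excluding a rise, while 8.1 speaks of detecting one. In a safety study, a non-significant pre/post test could be reported as reassurance when the data do not exclude the rise the protocol set out to examine.

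**Working it through.** **The plan's own figure.** The 20% rise is 0.20 × 1.2 = 0.24 mmol/l. With SD 0.7, 90% power and two-sided 5%, n = (0.7 × (1.960 + 1.282) / 0.24)² = 89.4, so 90 patients, or 92 with the t distribution. One-sided 5% gives 73 or 75. The stated inputs do not reproduce 106. Nothing below depends on how 106 arose; it is used only as the planned size.

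**The level CI.** With SD 0.7 also assumed after the procedure, the half-width is 1.983 × 0.7 / √106 = 0.135 mmol/l. A post-procedure mean of 1.44 gives 1.305 to 1.575 whether the baseline mean was 1.20 (a 20% rise) or 1.44 (no rise). The precision of the rise cannot be recovered from two separate summaries, because it depends on the pre/post correlation r: the SD of the change is 0.7 × √(2(1 − r)). For r = 0.3, 0.5 and 0.7, the half-width of the mean change is 0.160, 0.135 and 0.104 mmol/l.

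**A test of zero change compared with a 20% limit.** Assumptions not in the documents: lactate is lognormal (mean 1.2, SD 0.7), so the log-SD is √ln(1 + (0.7/1.2)²) = 0.541, and the log-scale pre/post correlation ρ is 0.3, 0.5 or 0.7. With n = 106:

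| Quantity | ρ = 0.3 | ρ = 0.5 | ρ = 0.7 |
|---|---|---|---|
| SD of log(post/pre) = 0.541 × √(2(1 − ρ)) | 0.640 | 0.541 | 0.419 |
| Smallest observed ratio significant against no change, exp(1.983 × SD / √106) | 1.131 | 1.110 | 1.084 |
| Largest observed ratio with upper 95% limit below 1.20 (1.20 / row above) | 1.061 | 1.081 | 1.107 |
| True 10% rise: trials non-significant while the CI includes 1.20 | 41% | 23% | 3% |
| Power to exclude 1.20 if there is no change, one-sided 2.5% | 83% | 93% | 99% |
| The same, one-sided 5% | 90% | 96% | 99.7% |
| Patients showing a rise of at least 20% when there is no true change, 1 − Φ(ln 1.2 / SD) | 39% | 37% | 33% |

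The fourth row is simulated: a signed-rank test on raw differences, with the 95% CI of the geometric mean ratio from log values, 4,000 trials per column. A run of 10,000 gives 42/23/2%. The power rows use the noncentral t distribution.

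Rows two and three show the problem directly. At ρ = 0.5, an observed ratio between 1.081 and 1.110 is non-significant and does not exclude 20%. At ρ = 0.7, a ratio between 1.084 and 1.107 is significant although a 20% rise is excluded. The p-value against zero answers neither question.

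**Raw-scale check.** With an SD of change of 0.7 (r = 0.5), an observed mean rise of 0.13 mmol/l (10.8%) has a 95% CI of −0.005 to 0.265. That is non-significant, yet the upper limit is 0.265 / 1.2 = 22%.

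**The case against.** The best defence is that the intent is recoverable. Lactic acid is measured before and after, 11.1 reports continuous variables as mean and SD or median and IQR, and a pre/post test was probably meant. So it would go too far to infer that the plan yields nothing about the rise: a crude group rise can be read from the two summaries. What is missing is its precision and a rule against 20%, and no other section supplies them.

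Four stronger readings are tempting, and the documents do not support them:

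- *No primary sample is identified.* The wording of 11.1 and 11.2 matches the post-procedure column of the schedule and the same-day heading of 9.3, so a sample is implied. Some doubt remains, because 9.3 also extends to the period before discharge while the schedule lists discharge separately. Confirmation is needed.
- *Later samples are contaminated because patients with contrast-induced nephropathy suspend metformin.* That sentence stands under study withdrawal (10.2). Whether such patients contribute later values is not stated, and the issue largely falls away if the same-day sample is primary.
- *106 shows that a signed-rank calculation was intended.* Other unstated additions also give it, for example 90 / 0.85 = 105.9.
- *The study is too small.* Excluding 20% with 90% power needs 132 patients at ρ = 0.3 and one-sided 2.5%, but 108 at one-sided 5%, and 95 at ρ = 0.5 and one-sided 2.5%. The documents give neither the correlation nor the sidedness.

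The lognormal model and the correlations are assumptions. The mismatch between endpoint and interval depends on neither.

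**Conclusion.** The point holds and should be corrected before the data are examined. The endpoint is a rise from baseline, the only planned CI is for a level, and the stated null cannot be tested in one arm. The rise therefore has no interval and no comparison with 20%, and the safety conclusion would depend on a reading chosen afterwards.

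That much rests on the text alone. Its practical size depends on the assumed model: with a true 10% rise, the chance of a non-significant test that leaves 20% open runs from about 41% at correlation 0.3 to about 3% at 0.7. The finding is about what is estimated and tested; it does not show that the sample is inadequate.

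**What to change.** **In 11.1**, replace the CI of the level with the 95% CI of the within-patient change from baseline at the post-procedure sample, after confirming which sample that is, using a paired method. One suitable form is the geometric mean post/pre ratio, read against 1.20; a paired percent change with its CI would also serve. Report the other samples as secondary. Report the proportion of patients with a rise of at least 20%, with its CI, as descriptive only, since a third or more may cross that line with no true change.

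**In 11.2**, restate the null about that change. Say whether the aim is to detect or to exclude a 20% rise, and whether the comparator is the patient's own baseline or the historical cohort.

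**In 8.1**, if the aim is to exclude 20%, state the power with its assumed correlation and sidedness: 83/93/99% with a two-sided 95% CI, or 90/96/99.7% at one-sided 5%, for correlations 0.3/0.5/0.7 at n = 106. Restate the figure rather than enrol more.

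**Cost:** wording only, with the same patients and samples. The downside is that the result becomes a ratio or percent change rather than a level in mmol/l, and the stated power may fall below 90% if the correlation is low.
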